11.4 Ethical Compliance

The study should be conducted in compliance with the protocol (including subject information sheet and informed consent form) approved by the institutional review board (IRB) and Badan Pengawas Obat dan Makanan (BPOM). The study should be also conducted in compliance with Indonesian good clinical practice (CUKB) and basic principles of the Declaration of Helsinki.

11.5 Measures to Protect the Safety of Subjects

All investigators and sub-investigators will be thoroughly familiarized with the protocol and conduct the study in accordance with the protocol. The principal investigator must take prior measures, including countermeasures against unexpected

adverse events, etc. and required reports as well as sufficient training for sub-investigators.

11.6 Utilization and Publication of Study Results

By signing the study protocol, the sub-investigators agree that the results of the study may be used for the purposes of registration, publication, and information for medical and pharmaceutical professionals. The sponsor has the right to review the contents prior to publication of this study results in scientific congresses or journals.

11.7 Subject Confidentiality

Names of subjects will remain confidential, and subjects will be identified by the identification codes (screening numbers) for recording and assessment. The subjects will be informed that all study data will be stored on the computer and treated with strict confidentiality. The signed informed consent form will be retained by the principal investigator. The principal investigator should make a list of subject identification codes (screening numbers) and names and keep relevant records. The informed consent form and subject list will be retained for at least 3 years from the date of study completion or marketing approval.

11.8 Quality Control and Reliability Assurance

Monitoring will be performed to protect the right and welfare of subjects, to check the accuracy, completeness and verifiability of the reported study-related data in comparison with source documents, and to check whether the study is conducted in accordance with the approved protocol, Indonesian GCP and applicable regulations.

The sponsor (or sponsor's designee) or the monitor will monitor the study through regular site visits and contacts. The visit schedule will be settled in proper consultation between the investigator and the monitor.

The monitor will visit the study site to check the completeness and clarity of the entries on the CRF, compare them with source data, and check administrative duties, and the investigator should cooperate with them. During the monitoring visit, the monitor will review the informed consent form, patient recruitment and follow-up, records and reports of SAEs, IP assignments, patient's compliance with the dose and regimen of the IP, the quantity of IPs, concomitant treatments, and data quality, with the investigators.

In order to guarantee the reliability during the study, the sponsor may perform audits, in addition to the general monitoring. An audit will include checking on whether this study is conducted in compliance with the protocol, standard operating procedure, and applicable regulations including the Indonesian GCP, and review of all source data, drug records, medical records, etc. The sponsor (or sponsor's designee) may require access to the source documents and other essential documents for the audit of the study site, and the investigators should allow such access and cooperate in the process.

Regulatory authorities may perform inspection at any time during the study or at the end of the study. In the event of audit or inspection, the investigators (and sites) will allow the auditor and inspector direct access to relevant data, and agree to allocate time of investigators themselves or other personnel, and to cooperate for discussion of issues found or related matters.

11.9 Protocol Approval

The study can be initiated after the protocol and other related documents are submitted to and approved by the Indonesian Food and Drug Authority (BPOM) and the IRB.

11.10 Protocol Amendment

Neither the principal investigator nor the sponsor can modify the contents of the protocol during the course of the study without the consent of the other. Once the study is initiated, amendment can be made only in exceptional cases. To modify the protocol, all involved parties must provide written consent by signature. In order to amend the approved study, the approval of the IRB should be obtained for the amended protocol and if necessary, an approval from the Minister of Food and Drug Safety should be obtained.

12 Sponsor Information, and Name and Title of Principal Investigator

12.2 Name and Title of Principal Investigator

Refer to Appendix 1. List of Study Sites and Principal Investigators

13 Other Matters Required to Conduct the Study Safely and Scientifically

13.1 Study Site

The head of a study site should fully prepare study facilities and specialized personnel needed for conducting the study for each study phase and be ready for the proper conduct of the study.

13.2 Principal Investigator

The principal investigator will be fully familiar with the solicited adverse events and precautions in the protocol in advance, and immediately notify the Institutional Review Board and the sponsor of any serious adverse events, etc. during the study.

13.3 Sub-Investigators

The sub-investigators will be fully familiar with the solicited adverse events and precautions for use in the protocol in advance, and immediately notify the principal investigator and the sponsor of any serious adverse events, etc. during the study.

13.4 Understanding of Protocol

The principal investigator and sub-investigators should thoroughly understand the protocol, and then conduct the study.

13.5 Protocol Deviation

If any protocol deviation becomes known during the study, the investigator should notify the deviation to the sponsor as soon as possible and decide whether to continue participation of the subject in the study. The followings are regarded as major protocol deviations:

- 1) Violation of inclusion and exclusion criteria
- 2) Administration of prohibited concomitant medications/therapies that may affect the study results
- 3) Treatment compliance of <80% or >120%
(Treatment compliance refers to the mean treatment compliance throughout the study treatment period for Fexuprazan 40 mg).
- 4) Other deviation considered as a major protocol deviation

For other minor deviations, the degree and reason of deviation or delay will be described accurately, and consideration on whether the study has been affected will be made at the time of result analysis.

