7.3.3 Treatment Compliance

In order to ensure the validity of research data related to the ability of IP to relieve symptoms and ensure safety in subjects, also to gain a better understanding of drug performance in real-world settings and improve the quality of study outcomes, at each visit after the administration of the IP, all subjects should return the unused IP prescribed at the previous visit and empty packaging, and the sub-investigator (or a designee) will check the number of tablets/capsule to be taken, number of tablets/capsules actually taken, and number of returned and unreturned tablets/capsules and record them on the case report form at each visit.

$$\text{Treatment compliance (\%)} = \frac{\text{Number of tablets/capsules actually taken}}{\text{Number of tablets/capsules to be taken}} \times 100$$

8 Study

Procedures and Assessments

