9.1 Analysis Sets

Per Protocol Set (PPS)

The PPS will include the subjects in the FAS who complete the study without any major protocol deviation. Major protocol deviations include 'violation of the inclusion and exclusion criteria', 'administration of prohibited concomitant medications during the study', etc. (see Section "13.5 Protocol Deviations"), and the subjects with other major deviations will be determined at the case report adjudication meeting prior to disclosure of randomization codes.

Full Analysis Set (FAS)

The FAS will include the subjects who receive the IP at least once after randomization and who have at least one efficacy assessment result. The subjects who violate the inclusion/exclusion criteria will be excluded from the FAS.

For the efficacy analysis, they will be included in the randomized treatment group regardless of the actual IP taken.

Safety Set

The safety set will include all the subjects who receive the IP at least once after randomization. The subjects who are enrolled in the study but withdrawn from the study before IP administration will be excluded from the safety set. For the safety analysis, the subjects will be analyzed according to the treatment they actually received.

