9.2 Statistical Analysis Method

9.2.1 General Principles of Result Analysis

The efficacy analysis will be conducted primarily on the PPS and FAS, and the PPS will be the primary analysis set.

In principle, all statistical analyses will use SAS® version 9.4 or higher and be performed with a two-sided test at a significance level of 5%, unless otherwise specified.

Descriptive statistics (mean, standard deviation, median, minimum, and maximum) will be calculated and provided for continuous variables, and the frequency and percentage will be provided for categorical variables.

The last observation carried forward (LOCF) method will be applied for correction of missing data of continuous endpoints among efficacy endpoints, and if the LOCF method cannot be applied, the raw data will be analyzed without correcting the missing data. However, the quality-of-life score (GERD-HRQL) will be analyzed using the raw data without applying the LOCF. For survival analysis, censoring will be utilized. When applying the LOCF, if the value immediately before the missing value is the baseline value, it will not be replaced.

The missing values of efficacy endpoints will be handled for both analyses on the FAS and PPS, and the safety endpoints will be analyzed with the raw data without replacing the missing values.

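### The compliance rule that feeds the primary per-protocol set is defined for the fexuprazan arm only (section 13.5)

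*Combined protocol and SAP*

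**What the plan says.** Item 3 of the major-deviation list in section 13.5 is compliance below 80% or above 120%. A parenthesis under it defines the term: "Treatment compliance refers to the mean treatment compliance throughout the study treatment period for Fexuprazan 40 mg". Item 4 is a catch-all without a threshold: "Other deviation considered as a major protocol deviation".

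Section 9.1 refers to 13.5 and states: "The PPS will include the subjects in the FAS who complete the study without any major protocol deviation". Other major deviations are to be settled at an adjudication meeting before the randomization codes are disclosed. Section 9.2.1 says: "The efficacy analysis will be conducted primarily on the PPS and FAS, and the PPS will be the primary analysis set".

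Section 7.3.3 collects compliance in both arms: "all subjects should return the unused IP prescribed at the previous visit and empty packaging", and staff record the "number of tablets/capsules actually taken, and number of returned and unreturned tablets/capsules". It gives the compliance formula but no limit. The only capsule in the trial is esomeprazole (6.1.2).

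**The concern.** A per-protocol set should be built by the same rule in each randomized arm. Here the only definition attached to the 80%/120% limit names one product. A programmer who follows 13.5 literally would drop fexuprazan poor compliers and keep esomeprazole poor compliers, unless the adjudication meeting removed the latter under item 4. That would put a fixed rule in one arm against case-by-case judgement in the other. The trial is open label (4.4), and the plan does not say that the adjudication listings will be masked.

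If poor compliers have less symptom relief than the rest, removing them from the fexuprazan arm alone raises that arm's observed proportion and leaves the control proportion where it is. The difference then moves towards non-inferiority in the set on which the primary conclusion is drawn.

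**Working it through.** **The plan's own figure.** Section 9.4.2 assumes 88.5% (control) and 94.0% (study), a margin of -0.1, one-sided alpha of 2.5% and a pooled Z-test. With 53 per group:

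- pooled proportion = (0.885 + 0.940)/2 = 0.9125
- null SE = √(0.9125 × 0.0875 × 2/53) = 0.0549
- alternative SE = √((0.940 × 0.060 + 0.885 × 0.115)/53) = 0.0546
- power = Φ[(0.055 + 0.10 - 1.96 × 0.0549)/0.0546] = 0.807

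This matches the stated 0.80729. At 52 per group the power is 0.79984, so 53 is right, and 53/0.8 rounds up to 67 per group, 134 in total. The sample size is not in dispute.

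**Bias from a one-arm exclusion.** Let f be the share of poor compliers and g the gap in relief (compliers minus poor compliers). If the whole arm has relief p, the compliers have p + f × g. Removing poor compliers from fexuprazan only therefore shifts the difference by f × g. Removing them from both arms, with the same f and g, leaves the difference unchanged.

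**Chance of a false non-inferiority claim.** The true proportions are set at the margin: 0.885 for control and 0.885 - 0.10 = 0.785 for fexuprazan, with 53 per group before exclusion. Success means a lower 95% limit above -0.1. The plan names a chi-square or Fisher test but no interval formula, so Newcombe limits are assumed. All binomial outcomes were enumerated.

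- One-arm rule: n_T = round(53(1 - f)), p_T = 0.785 + f × g; n_C = 53, p_C = 0.885.
- Both-arm rule: n_T = n_C = round(53(1 - f)), with f × g added to both proportions.

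Both f and g are assumptions; the documents give neither.

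| f | g (points) | Fexuprazan subjects removed | Shift f × g (points) | One-arm rule | Both-arm rule |
|---|---|---|---|---|---|
| 0 | – | 0 | 0 | 2.5% | 2.5% |
| 2% | 20 | 1 | 0.4 | 3.0% | 2.6% |
| 5% | 20 | 3 | 1.0 | 3.7% | 2.3% |
| 5% | 30 | 3 | 1.5 | 4.2% | 2.3% |
| 10% | 30 | 5 | 3.0 | 6.4% | 2.5% |
| 20% (extreme) | 40 | 11 | 8.0 | 17.6% | 1.9% |

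With g = 0 the one-arm rule gives 2.7%, 2.7% and 2.2% at f = 5%, 10% and 20%; these small departures come only from the changed group size. With a negative gap (poor compliers do better) the rule is conservative: 2.3% at 5%/-10 points, 2.0% at 5%/-20 points and 1.4% at 10%/-20 points.

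**Sensitivity to the method.** With Wald limits and 67 per group, at f = 10% and g = 30 points, the figures are 8.2% (one arm), 3.2% (both arms) and 3.0% (no exclusion). The pattern does not depend on the choice of interval.

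**The case against.** The strongest reply is that the one-arm reading is not the intended one. The threshold line in 13.5 names no arm, 7.3.3 defines compliance for tablets and capsules in all subjects, and the schedule checks compliance in everyone. The parenthesis may be meant only to say that compliance is averaged over the treatment period. That is likely, but the parenthesis is the only definition attached to the limit, and nothing in the document overrides it.

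Second, adjudication takes place before code disclosure, and 4.4 keeps the code under controlled access. This is some protection. It is limited where the treatment is known at the site and the product is labelled as study or control drug (6.3), and item 4 supplies no threshold to apply.

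Third, the per-protocol set already requires completion of the study. Early stoppers leave both arms, so only non-compliance among completers matters. That stands, and it makes the 10% and especially the 20% cases less likely.

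Fourth, the direction is not certain. Subjects who feel well may skip doses, and the rule would then count against fexuprazan. This also stands.

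Fifth, the full analysis set has no compliance exclusion and is analysed too. It is a useful check but not the primary set, and the plan does not say what follows if the two sets disagree. That gap is a separate matter, which the edit proposed here would not close.

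**Conclusion.** The concern holds. As written, the fixed compliance limit for the primary analysis set covers one arm of a non-inferiority comparison. With 2% to 5% poor compliers and a 20-point gap, the error at the margin is about 3.0% to 3.7% against 2.5%. It becomes material only if poor compliance is more common and the gap larger (6.4% at 10% and 30 points). The direction favours fexuprazan only if poor compliers have less relief. All of these figures rest on assumed shares and gaps and on an assumed interval method. The wording is probably a slip, but it governs who enters the primary set, so it should be corrected and not left to interpretation at data review.

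**What to change.** In the parenthesis of 13.5, replace the reference to fexuprazan with *for the assigned investigational product (either arm)*, calculated by the formula in 7.3.3. The plan's own limits of 80% and 120% then define the per-protocol set in both arms. Make the change before data review.

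The cost is one phrase. The counts are already collected in both arms, and 53 per group and 134 in total are unchanged. A few esomeprazole poor compliers would also leave the per-protocol set, about 3 of 53 if 5% are non-compliant (0.05 × 53 = 2.65), which widens the confidence interval slightly.

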13.6 Criteria for the Subject's Medical Care and Treatment after the Study

Subsequent medical care and treatment for subjects who terminate the study early or complete the study will be in accordance with general principle of medical care and treatment of a patient with gastroesophageal reflux disease.

However, if the subject is injured from the treatment or clinical procedure which would not have been performed if the subject has not participated in the study, he/she will receive every treatment according to the standard processes of the hospital. If the injury is related to the study, the cost will be covered in accordance with the participant compensation rule and the sponsor's insurance conditions of the study.

13.7 Independent Data Monitoring Committee

The study will not constitute a separate Independent Data Monitoring Committee (IDMC).

13.8 Expected Adverse Events Caused by the Investigational Product and Precautions for Use

13.8.1 Expected Adverse Events of Fexuprazan

The adverse events predicted from the results of phase 1 and phase 2 studies of Fexuprazan performed so far are as follows.

1) Phase 1 Study (DW_FEXUPRAZAN001)

A dose block-randomized, double-blind, placebo- and active-controlled, single and multiple dosing, dose-escalation clinical phase 1 trial to investigate the safety, tolerability, pharmacokinetics and pharmacodynamics of Fexuprazan after oral administration in healthy male volunteers was conducted. A total of 28 and 35 adverse events occurred in single and multiple dosing studies, respectively, and they were all mild in severity and recovered without any actions taken. Among them, the adverse drug reactions for which possible relationship to the FEXUPRAZAN cannot be ruled out are:

Study	Dose group	Adverse drug reaction term	Severity
Single Dosing Study	FEXUPRAZAN 20 mg	Epigastric discomfort Dyspepsia	Mild Mild
	FEXUPRAZAN 80 mg (fasting)	Headache	Mild
	FEXUPRAZAN 80 mg (fed)	Vomiting (2 events) Headache	Mild Mild
	FEXUPRAZAN 160 mg	Nausea	Mild

Multiple Dosing Study	FEXUPRAZAN 40 mg	Abdominal distension Abdominal pain Skin exfoliation Headache	Mild Mild Mild Mild
	FEXUPRAZAN 80 mg	Blood creatine phosphokinase increased Abdominal discomfort	Mild Mild

2) Phase 2 Study (DW_FEXUPRAZAN002)

A multi-center, randomized, double-blind, active-controlled, phase 2, therapeutic exploratory study was conducted to evaluate the efficacy and safety of Fexuprazan in patients with erosive gastroesophageal reflux disease. The result of safety assessment showed that 63 adverse events occurred in 36 out of 156 subjects who were treated with Fexuprazan, 24 events of which were adverse drug reactions occurring in 13 subjects. Among them, the adverse drug reactions for which possible relationship to the Fexuprazan cannot be ruled out are:

Dose group	Adverse drug reaction term	Severity
FEXUPRAZAN 20 mg	Nausea Abdominal pain Urticaria Oesophageal candidiasis	Mild Mild Mild Mild
FEXUPRAZAN 40 mg	Nausea Abdominal discomfort Headache Erythema Myalgia Feeling abnormal	Mild Mild Mild Mild Mild Mild
FEXUPRAZAN 80 mg	Headache Dizziness (2 events) Rash (2 events) Alanine aminotransferase increased (3 events) Aspartate aminotransferase increased (3 events) Blood lactate dehydrogenase increased Gamma-glutamyltransferase increased Myalgia	Mild Mild Mild Mild Mild Mild Mild Mild

14 Reporting and Publication

14.1 Clinical Study Report

The data and information collected during this study will be reported in a study report prepared by the CRO. Sponsor and Daewoong Pharmaceutical Co, Ltd will be provided the information regarding study product. The final report may be used for the further development of the investigational product as considered necessary by the Sponsor and/or Daewoong Pharmaceutical Co.,Ltd.

14.2 Confidentiality and Intellectual Property Rights of Study Data

Any confidential information relating to the investigational product or the study, including any data and results from the study will be the exclusive property of the Sponsor and Daewoong Pharmaceutical Co.,Ltd. The Investigator and any other persons involved in the study will protect the confidentiality of this proprietary information belonging to the Sponsor.

Attachment 2. Gastroesophageal Reflux Disease Questionnaire (GERD-Q)

Screening No.	__S__	Subject No.	__R__			
Subject initial						
Visit No.	 Visit 1	 Visit 2	 Visit 3	 Visit 4	 Visit 5	 Early withdrawal or unscheduled visit

Cobalah mengingat apa yang Anda rasakan dalam 7 hari terakhir						
Berikan tanda centang (v) hanya pada satu tempat untuk setiap pertanyaan dan hitunglah poin GERD-Q Anda dengan menjumlahkan poin pada setiap pertanyaan.						
No.	Pertanyaan	Frekuensi dari skor (poin) untuk gejala				
		0 hari	1 hari	2-3 hari	4-7 hari	
1.	Seberapa sering Anda mengalami perasaan terbakar di bagian belakang tulang dada Anda (heartburn)?	 0	 1	 2	 3	
2.	Seberapa sering Anda mengalami naiknya isi lambung ke arah tenggorokan/mulut Anda (regurgitasi)?	 0	 1	 2	 3	
3.	Seberapa sering Anda mengalami nyeri ulu hati?	 3	 2	 1	 0	
4.	Seberapa sering Anda mengalami mual?	 3	 2	 1	 0	
5.	Seberapa sering Anda mengalami kesulitan tidur malam oleh karena rasa terbakar di dada (heartburn) dan/atau naiknya isi perut?	 0	 1	 2	 3	
6.	Seberapa sering Anda meminum obat tambahan untuk rasa terbakar di dada (heartburn) dan/atau naiknya isi perut (regurgitasi), selain yang diberikan oleh dokter Anda? (seperti obat maag yang dijual bebas)	 0	 1	 2	 3	
Hasil		Bila poin GerdQ Anda \leq 7, kemungkinan Anda tidak menderita GERD Bila poin GerdQ Anda 8-18 , kemungkinan Anda menderita GERD				

*) The Gastroesophageal Reflux Disease Questionnaire has been validated by Marcellus Simadibrata, Aziz Rani, Pangestu Adi, Ali Djumhana, Murdani Abdullah with an article titled “The gastro-esophageal reflux disease questionnaire using Indonesian language: a language validation survey” at May 2011.

Documented date	Date Month Year 20	Documented by	(Signature)
Reviewed date	Date Month Year 20	Documented by	(Signature)

Attachment 3. Quality of Life Questionnaire (GERD-HRQL; GERD-Health Related Quality of Life)

Screening No.	__ S __	Subject No.	__ R __		
Subject initials					
Visit No.	 Visit 2	 Visit 3	 Visit 4	 Visit 5	 Early withdrawal or unscheduled visit

Check each applicable item in the below check boxes.

0 poin	Tidak ada gejala
1 poin	Gejala terlihat tapi tidak mengganggu
2 poin	Gejala terlihat dan mengganggu tapi tidak setiap hari
3 poin	Gejala mengganggu setiap hari
4 poin	Gejala mempengaruhi aktivitas sehari-hari
5 poin	Gejala menyebabkan ketidakmampuan untuk melakukan aktivitas

For each question, what score best describes your symptoms?

1	Seberapa buruk rasa terbakar di dada Anda?	 0	 1	 2	 3	 4	 5
2	Rasa terbakar di dada saat berbaring?	 0	 1	 2	 3	 4	 5
3	Rasa terbakar di dada saat berdiri?	 0	 1	 2	 3	 4	 5
4	Rasa terbakar di dada setelah makan?	 0	 1	 2	 3	 4	 5
5	Apakah rasa terbakar di dada mengubah diet Anda?	 0	 1	 2	 3	 4	 5
6	Apakah rasa terbakar di dada membuat Anda terbangun dari tidur?	 0	 1	 2	 3	 4	 5
7	Apakah Anda mengalami kesulitan menelan	 0	 1	 2	 3	 4	 5
8	Apakah Anda memiliki perasaan kembung atau perasaan penuh dengan gas?	 0	 1	 2	 3	 4	 5
9	Apakah Anda memiliki rasa sakit saat menelan?	 0	 1	 2	 3	 4	 5
10	Jika Anda minum obat, apakah ini mempengaruhi kehidupan sehari-hari Anda?	 0	 1	 2	 3	 4	 5
11	Seberapa puas anda dengan kondisi anda saat ini?	 Satisfied		 Average		 Not satisfied	

*) The GERD Health Related Quality of Life Questionnaire has been validated by Laura A. Siahaan, [name], Marcellus Simadibrata, Siti Setiati with an article titled “The Validity and Reability Test of the Indonesian version of Gastroesophageal Reflux Disease Quality of Life (GERD QOL) Questionnaire” at January 2017.

Documented date	Date Month Year 20	Documented by	(Signature)
Reviewed date	Date Month Year 20	Documented by	(Signature)

